#### Planned recruitment rate

It is expected that sites will recruit 2 patients per month on average.

#### Statistical analysis

#### Overview

We will undertake both a frequentist and Bayesian analysis on the primary outcome and a frequentist analysis on all secondary outcomes. For the primary outcome no multiple imputation will be used for missing outcome data as it is anticipated missing data will be extremely low due to the ability to retrieve information from routinely collected clinical data within medical records. The Bayesian analysis on the primary outcome will be used to facilitate interpretation and we will use vague prior distributions on the model parameters including the treatment effect parameter. In the frequentist approach we will report the Summary statistic (e.g. Odds Ratio) with 95% confidence intervals and the interpretation will focus on the magnitude of the intervention effect and precision of this estimate. In the Bayesian analysis we will report the probability of superiority, and the probability of superiority by a meaningful margin which will be pre-specified in the statistical analysis plan after consultation with Patient and Public Involvement and Engagement (PPIE) members and clinical teams.

For secondary outcomes where missing outcome data is greater than approximately 5% we will undertake multiple imputation and the model will be specified in the statistical analysis plan and will include the outcome as well as stratification variables.

#### Internal Pilot & success criteria.

We will undertake an internal pilot after 8 months from the start of recruitment when approximately 350 participants should have been recruited. We will also examine the internal pilot outcomes at 4 months to allow early corrective action if required but the trial will not be stopped based on this review.

We will assess recruitment to the trial for each of the three trials. These will be reviewed by the CI, the Trial Steering Committee and the funder. The criteria in Table 4 will be used to assess the pilot trial. If all three intervention arms meet the red criteria stopping the trial will be considered by the CI, the Sponsor and the Funder.

Sponsor: Imperial College London

Version 1.1 22-Aug-2023

Table 4: The progression criteria to be assessed by the study team, TSC and funder

Progression criteria	Recruitment Criteria at 8 months	Proportion stopping antibiotics when PCT & PCR tests are both negative in diagnostic trial	in total fluid balance
RED: Consider stopping the affected trial	Recruitment rate is less than 40% of planned	<40%	<250ml
AMBER: Explore methods to increase recruitment to the affected trial	Recruitment rate is between 40% and 95% of planned	40-80%	≥250ml and <750ml
GREEN: Continue without changes	Recruitment rate is ≥95%	>80%	≥750ml

The TSC will also informally monitor measures of adherence and data quality:

- The median time (and IQR) to the PCR results being available in the intervention arm of the diagnostic trial
- The proportion of participants who receive at least 50% and 75% of the drug or placebo in the GM-CSF trial
- Completeness of clinical state data over time

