# Diagnostic trial

Intervention – antibiotic optimisation using PCR-based pathogen testing and procalcitonin

A blood sample will be taken after randomisation for rapid PCR-based pathogen testing, to be sent to the designated molecular diagnostic laboratory.

Procalcitonin (PCT) will be measured on the day of inclusion and the next day (18 - 36 hours later). This will be measured in the local hospital laboratory or using a point of care device. If a sample has already been sent as part of clinical care on the day of inclusion that value can be used for trial purposes; it does not have to be repeated.

In addition, all standard microbiological sampling will continue as normal.

If the **PCR result is positive**, the antibiotic regimen will be optimised based on this result. The result from the PCR result will be sent to sites from the central coordination centre. The clinical team should seek advice from their local microbiology service as appropriate to discuss optimal antibiotic choice based on local sensitivity and resistance patterns of the identified organism(s).

If the PCR result is negative AND the procalcitonin results are negative (both results <0.5 µg/L or the second procalcitonin result has dropped by >80% from the first result) and there are no other positive microbiology results or clear objective evidence for infection, then the empiric antibiotics will be stopped. As well as standard microbiology culture techniques, other sources of evidence for infection, based on usual practice will be reviewed. These include pneumococcal and Legionella antigen tests, white cells on lumbar puncture, purpuric rash or evidence of faecal soiling seen at laparotomy. If any of these objective features of infection are present antibiotics will be continued according to local guidelines.

In all other patients (including if PCR is negative and the procalcitonin is positive, i.e. ≥0.5 µg/L without an 80% drop from first to second result), antibiotic prescriptions will be reviewed daily, in consultation with microbiology teams. Sites are advised to both de-escalate antibiotic therapy and prescribe short courses of antibiotics, as clinically appropriate, as recommended by Public Health England.(42)

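### The pilot's antibiotic-stopping criterion uses two of the three conditions in the stopping rule, so patients managed exactly to protocol count against the diagnostic trial

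*Protocol*

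**What the plan says.** The intervention text for the diagnostic trial (Protocol section 6, Treatment) sets the stopping rule. The first part is that the "PCR result is negative AND the procalcitonin results are negative". The sentence then adds a further requirement: "and there are no other positive microbiology results or clear objective evidence for infection, then the empiric antibiotics will be stopped". Examples of other evidence follow: "These include pneumococcal and Legionella antigen tests, white cells on lumbar puncture, purpuric rash or evidence of faecal soiling seen at laparotomy". The instruction for patients who have such evidence is explicit: "If any of these objective features of infection are present antibiotics will be continued according to local guidelines".

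The progression criteria (Protocol section 9, Internal Pilot, Table 4) include one column for this trial: "Proportion stopping antibiotics when PCT & PCR tests are both negative in diagnostic trial". The bands are below 40%, 40-80% and above 80%. The lowest row carries the action "RED: Consider stopping the affected trial". The review falls at 8 months, "when approximately 350 participants should have been recruited". The section on early discontinuation (section 13) describes the internal pilot as the trial's only formal source of stopping rules.

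Table 4 does not mention the third condition, and nothing elsewhere in the protocol narrows its denominator.

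**The concern.** The rule that sites follow has three conditions and the criterion that judges them has two. A dual-negative patient with, say, a positive antigen test is continued as the protocol directs, and Table 4 counts that patient as a failure to stop.

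The score therefore mixes case-mix with adherence. A result of 70% could mean full adherence with 30% of dual-negative patients having other evidence. It could equally mean 70% adherence with no such patients. The steering committee and funder could not tell these apart from the column as defined, although they call for different responses. The criterion feeds a formal progression decision. A score below GREEN could prompt corrective action for a problem that sites do not have.

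**Working it through.** **Inputs from the protocol**

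- Bands (Table 4): GREEN above 80%, AMBER 40-80%, RED below 40%. No derivation is given, so there is no stated figure to reproduce.
- Pilot size: about 350, hence about 350 / 2 = 175 in the PCR/PCT arm at 1:1 allocation.

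**Inputs the protocol does not give (assumptions)**

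- q, the observed share of dual-negative patients with other evidence of infection. A range is shown.
- m, the number of dual-negative patients at the 8-month look. Values of 20, 40 and 60 are used, which are 11%, 23% and 34% of 175.
- Patients continued because of other evidence are not counted as having stopped.

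**Step 1: score on the denominator as written.** Let a be adherence among patients who meet the full rule. Then

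score = a × (1 - q), and with a = 1, score = 1 - q.

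| Observed q | Score at full adherence | Band |
|---|---|---|
| 10% | 90% | GREEN |
| 19% | 81% | GREEN |
| 20% | 80% | AMBER (GREEN requires more than 80%) |
| 30% | 70% | AMBER |
| 50% | 50% | AMBER |
| 60% | 40% | AMBER |
| 61% | 39% | RED |

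Below 20% the bar still moves. At q = 10%, GREEN needs a above 0.80 / 0.90 = 88.9%.

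**Step 2: chance of each band at full adherence.** The observed q varies by chance around an expected share p. The number stopping is then binomial with size m and probability 1 - p. GREEN needs at least 17 of 20, 33 of 40 or 49 of 60.

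| Expected share p | P(AMBER), m = 20 | P(AMBER), m = 40 | P(AMBER), m = 60 |
|---|---|---|---|
| 10% | 13% | 4% | 2% |
| 15% | 35% | 24% | 18% |
| 20% | 59% | 56% | 55% |
| 30% | 89% | 95% | 97% |

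P(RED) is about 0.1% or less for every p up to 30%. At p = 50% it is 13%, 8% and 5% for m = 20, 40 and 60.

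**Step 3: score on the full-rule denominator.** With patients who have other evidence removed from the denominator, score = a. Full adherence scores 100% whatever q is, and the bands then measure adherence alone.

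**The case against.** **Table 4 may be shorthand for the full rule.** That is possible. As written, though, the column heading names two conditions and the treatment text names three, and whoever programs the measure will work from the heading.

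**The column may be meant to show whether the intervention changes care, not pure adherence.** The neighbouring fluid-balance column is not a pure adherence measure either. If few dual-negative patients stop for any reason, the stopping pathway has little effect, and that matters for progression. This is a fair reason to keep the all-dual-negative figure in view. It does not remove the contradiction, because patients treated as the protocol directs would still be scored as failures. The gap between 80% and 100% may leave room for justified continuation, but the protocol does not say so and gives no q to size it.

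**The consequences are softened.** RED prompts consideration, not automatic stopping. Stopping the whole trial is considered only if all three arms are RED, and the 4-month look is for corrective action only. The protocol also says that, where possible, CRFs will capture the interventions' effect on decisions, so reasons for continuing may already be recorded. All of this stands and limits the seriousness of the point.

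**The two-test denominator is more objective.** Other evidence is judged locally from an open list of examples. A denominator that depends on it could let non-stoppers be removed by citing evidence. This stands, and it is why both figures should be reported.

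**Conclusion.** The mismatch is plain in the text and the 1 - q ceiling follows directly. A fully adherent diagnostic trial cannot score GREEN once the observed share of dual-negative patients with other evidence is 20% or more. It is worth correcting before the 8-month look, but it does not threaten the main analysis.

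A reader might infer three stronger things, and the protocol supports none of them.

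- *That perfect adherence is likely to score RED.* This needs an observed q above 60%, and no figure in the protocol points to such a value. AMBER is the realistic risk.
- *That q is about 30%, from the Background's statement that blood cultures are informative in fewer than 30% of patients.* That figure is an upper bound for sepsis patients in general. The relevant patients have already been selected as negative on both PCR and procalcitonin, which should remove many who are culture-positive. It should not be used for q.
- *That GREEN is out of reach whenever 20% or more of patients are expected to have other evidence.* The ceiling applies to the observed share. At an expected 20% with 40 patients, GREEN still occurs about 44% of the time.

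The AMBER probabilities are illustrations that rest on assumed p and m. This is a point about measurement only and takes no position on when antibiotics should stop.

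**What to change.** Reconcile Table 4 with the diagnostic trial's treatment text. Define the denominator as patients who meet the full stopping rule: PCR negative, procalcitonin negative, and the third condition that "there are no other positive microbiology results or clear objective evidence for infection". Beside it, report the proportion stopping among all dual-negative patients, the number continued, and the recorded reason for each.

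The cost is one table heading and, if the CRF does not already capture it, one item for the reason for continuing. The downside is a smaller denominator at the 8-month look that depends partly on local judgement of what counts as objective evidence. Reporting both figures makes that dependence visible: a large gap between them would show the committee how much of the result rests on exclusions.

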### **Estimand Definitions and Analysis on Primary Outcome**

In randomised trials the occurrence of important post randomisation events that impact the outcome can create ambiguity as to what intervention effect has been estimated if they are not defined and well described as to how they have been handled in the analysis. In order to address a precisely defined research question as recommended by ICH-E9 guidelines, (48) we define the five attributes of the primary estimand so that there is clarity for which intervention effect is the primary one to be estimated. We will perform a sensitivity analysis on the primary estimand to examine the impact of any statistical assumptions. We will also undertake supplementary analysis on the primary outcome.

The estimands for the diagnostics, fluids and GM-CSF trials are set out in Supplementary Tables A, B and C respectively. Potential additional exploratory estimands are set out in Supplementary Table D. The key features of the estimands are summarised below.

Sponsor: Imperial College London

Version 1.1 22-Aug-2023

In the primary estimand for all three trials we aim to answer a 'treatment policy strategy' question how effective the intervention is compared to routine clinical practice regardless of intercurrent events such as intervention non-adherence, standard diagnostic results and co-enrolment to other trials.

#### Supplementary estimands for intercurrent events

For the diagnostics trial, a key post randomisation event in routine clinical practice is the routine blood culture result that informs subsequent treatment. Although the diagnostics intervention may benefit all patients due to its rapidity relative to the blood culture test, it is potentially of greatest benefit to those for whom the blood culture result does not identify a target pathogen. A supplementary estimand will therefore use a 'principal stratum' strategy to assess the effect of the diagnostics intervention in only those patients who do not receive a positive blood culture result.

For the fluids trial, the main post randomisation factor that may affect the interpretation of results is the occurrence of fluid overload, which may confound or mediate the intervention effect. However, this is not a discrete event but may occur to a varying extent throughout the trial, and its influence on the results will be assessed not with a supplementary estimand but via a mediation analysis based on the number of days of fluid overload and component of the intervention given.

The diagnostics and fluids trials involve complex, pragmatically defined interventions, and thus it is not feasible to capture treatment adherence as a discrete post randomisation event. The treatment policy strategy is thus the only practical approach to adherence for these trials, but where possible, the interventions' impact on decision making and patient care will be captured via CRFs to enable monitoring of the various aspects of treatment adherence.

For the GM-CSF trial, supplementary estimands will assess the effect of the intervention in participants with varying levels of adherence, defined by the number of doses of treatment received. This will enable the relationship between dosage and treatment effect to be explored graphically.

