#### 5.6.3 GM-CSF

Intervention / control – GM-CSF (sargramostim) / placebo

In the subset of patients requiring mechanical ventilation, or with two or more organ failures and with persistent lymphopaenia (defined as an absolute lymphocyte count <1.2 x10^9/L on two consecutive calendar days at least 12 hours apart, with no values >1.2 x10^9/L in between) subcutaneous GM-CSF (sargramostim) or a matching placebo will be given.

The dose will be 500µg (two vials) for patients ≥50kg, and 250µg (one vial) for patients <50kg, once a day for 8 days in the ICU.

If the patient is discharged from the ICU before the 8th day then the study drug should be given on the ward until 8 doses in total have been, if logistics allow. It will not be a protocol deviation if this is not possible. If the patient is discharged hospital before the 8th day then the study drug will stop.

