# **Drug interactions / Precautions / Contraindications**

Do not administer sargramostim (GM-CSF) to patients with a history of serious allergic reactions, including anaphylaxis, to human GM-CSF such as sargramostim, yeast-derived products, or any component of the product.

Sargramostim (GM-CSF) should be permanently discontinued if the total WBC count exceeds 50  $\times 10^9$  /L or if a serious allergic or anaphylactic reaction occurs.

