# SUPPLEMENTARY TABLE C: Primary and supplementary estimands for the GM-CSF trial

Attribute	Primary estimand	Supplementary estimand for intercurrent events	Supplementary estimand for concomitant treatments	
Population	Patients eligible for the GM-CSF trial	Patients eligible for the GM-CSF trial	Patients eligible for the GM-CSF trial	
Treatment condition(s)	GM-CSF intervention vs standard of care	GM-CSF intervention vs standard of care	Diagnostics intervention plus GM-CSF intervention vs diagnostics intervention alone; Fluids intervention plus GM-CSF intervention vs fluids intervention alone; All 3 interventions vs Diagnostics intervention plus fluids intervention	
Variable (outcome)	Mortality, in-ICU with organ support, in-hospital without organ support, discharged over 90 days	Mortality, in-ICU with organ support, in-hospital without organ support, discharged over 90 days	Mortality, in-ICU with organ support, in-hospital without organ support, discharged over 90 days	
Intercurrent events and the strategies used to handle them in the analysis	Intervention adherence and discontinuation – treatment policy 	Intervention adherence and discontinuation – principal stratum¹ (participants receiving >=n doses – each value of n giving rise to a different estimand)	Intervention adherence and discontinuation – treatment policy 	
	Receiving other SepTIC trial interventions – treatment policy  , or (for sensitivity analysis) principal stratum 	Receiving other SepTIC trial interventions – treatment policy  , or (for sensitivity analysis) principal stratum 	Receiving other SepTIC trial interventions – treatment policy  , or (for sensitivity analysis) principal stratum 	
	Use of other available treatments and medicines – treatment policy 	Use of other available treatments and medicines – treatment policy 	Use of other available treatments and medicines – treatment policy 	

<sup>2 A principal stratum strategy uses the intercurrent event as a means to target the population of interest in which to estimate the treatment effect eg the population that receive the intervention as intended

Sponsor: Imperial College London

Version 1.1 22-Aug-2023

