	Co-enrolment in other clinical trials - treatment policy 	Co-enrolment in other clinical trials - treatment policy 	Co-enrolment in other clinical trials - treatment policy 
Population-level summary measure	Odds Ratio from a proportional odds model across the 4 clinical states conditional on age and minimisation variables.	Odds Ratio from a proportional odds model across the 4 clinical states conditional on age and minimisation variables.	Odds Ratio from a proportional odds model across the 4 clinical states conditional on age and minimisation variables.
	Posterior Probability of being in a better clinical state using a Bayesian Proportional Odds model with vague priors.	Posterior Probability of being in a better clinical state using a Bayesian Proportional Odds model with vague priors.	Posterior Probability of being in a better clinical state using a Bayesian Proportional Odds model with vague priors.
Rationale for the estimand	The aim of the trial is to assess whether GM-CSF as given can improve on standard of care in the population of eligible patients.	If the trial does not demonstrate a positive result among the entire eligible population, it may still be of interest to assess the effect of the intervention in cases where treatment adherence is high.	If the diagnostic and/or fluids trials shows a positive result, then the fluids respective interventions may potentially be adopted as standard of care.

<sup>1 A treatment policy strategy considers the occurrence of the associated intercurrent event as irrelevant, and participant data are analysed regardless.

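### The GM-CSF adherence strata count raw doses, which death and discharge cut short, so a trend across dose count cannot be read as dose-response

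*Protocol*

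**What the plan says.** In Section 9 of the protocol, under supplementary estimands for intercurrent events, the rule for the GM-CSF trial is that "supplementary estimands will assess the effect of the intervention in participants with varying levels of adherence, defined by the number of doses of treatment received", and the stated use is: "This will enable the relationship between dosage and treatment effect to be explored graphically". Supplementary Table C implements this as a principal stratum of "participants receiving >=n doses", with a separate estimand for each n. Its rationale is that, if the overall result is not positive, it may still be useful to "assess the effect of the intervention in cases where treatment adherence is high".

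The dosing rules are elsewhere. Section 5.6.3 plans eight daily doses. If the patient leaves hospital before the eighth "day then the study drug will stop". After ICU discharge, dosing continues on the ward where logistics allow, and of a failure to do so the protocol says: "It will not be a protocol deviation if this is not possible". Section 7 adds that sargramostim "should be permanently discontinued if the total WBC count exceeds 50" x10^9/L. Death ends dosing in any case. In Section 9, discharge from hospital and death are states 1 and 4 of the primary outcome.

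**The concern.** A raw dose count mixes two things: whether due doses were given, and how long the participant remained alive and in hospital. Someone who receives every due dose and goes home on day 4, or dies on day 4, has complied fully with the protocol, yet falls outside every stratum that needs more doses than could be given by then. With perfect adherence, reaching n doses means only being alive and in hospital on dosing day n. The strata therefore select on early values of the primary outcome and do not isolate the highly adherent participants named in the rationale.

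The estimand is offered for the case where the main result is not positive, which is when a graph of effect against dose is most likely to be over-read. Table C also does not say whether the dose threshold applies to placebo doses as well.

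**Working it through.** **The plan's own figure.** The protocol gives no figure for this estimand. Its GM-CSF sample size reproduces: 45% against 36%, 90% power and two-sided 5% need 624 per arm, 1,248 in total; 1,248 / 0.98 = 1,274 after 2% loss, close to the stated 1,300. The 9-point target difference serves as a yardstick below.

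**Share unable to reach eight doses with perfect adherence.** Table 2 (control arm, whole sepsis population) has 5% dead and 6% discharged at day 7: 0.05 + 0.06 = 0.11. Day 7 stands in for the days before the eighth dose.

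**False benefit under no effect if GM-CSF participants with at least eight doses are compared with all placebo.** Let M be 90-day mortality, d the share dead by day 7 and h the share discharged by day 7, with no later deaths among those discharged. Mortality in the eight-dose group is (M - d) / (1 - d - h).

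- Table 2 as it stands: (0.30 - 0.05) / 0.89 = 28.1% against 30%, a difference of -1.9 points. Odds ratio (0.281/0.719) / (0.30/0.70) = 0.91.
- Scaled to the GM-CSF subset (assumption: d = 0.05 x 45/30 = 0.075), h = 6%: 0.375 / 0.865 = 43.4% against 45%, -1.6 points, odds ratio 0.94.
- Scaled, h = 0: 0.375 / 0.925 = 40.5% against 45%, -4.5 points, odds ratio 0.83.
- Scaled, but 20% leave ICU early and receive no ward doses (assumption): 0.375 / 0.725 = 51.7%, odds ratio 1.31; about 1.24 if 5% of those leaving die later. The sign reverses.

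**Same threshold in both arms.** A daily death and discharge simulation was run with 1,000,000 per arm and every due dose given. Assumptions: normally distributed frailty with SD 1; placebo arm with 7.4% dead and 6.0% discharged by day 7 and 47.6% dead by day 90. Mortality odds ratios:

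| Scenario | at least 1 dose | at least 4 | at least 8 |
|---|---|---|---|
| No effect | 1.00 | 1.00 | 1.00 |
| Death hazard ratio 0.7 throughout | 0.76 | 0.77 | 0.78 |
| Hazard ratio 0.5 in days 1-8 only | 0.95 | 0.99 | 1.03 |
| Hazard ratio 0.7 after day 8 only | 0.79 | 0.78 | 0.76 |

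Nobody missed a due dose, so any movement across a row comes from who remains in the stratum. Under no effect but against all placebo, the same simulation moves from 1.00 at one dose to 0.94 at eight.

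**The case against.** A reader might infer that the graph must show a false dose trend. The documents do not support that. Placebo is matching and blinded, and the Trial Steering Committee's informal adherence measure counts doses of drug or placebo, so the same threshold can be used in both arms. There is then no trend under the null and almost none under a constant hazard ratio. The all-placebo comparison is one reading that the text leaves open; the protocol does not specify it.

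A reader might also infer a distortion as large as the 9-point target. At 45% mortality with no early discharges, that needs (0.45 - d) / (1 - d) = 0.36, so d = 0.09 / 0.64 = 14% dead before the eighth dose. Table 2 has 5%, or 7.5% when scaled.

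It is fair to add that Table C names a principal stratum, which is defined by potential and not observed receipt, and that the estimator may properly be left to the statistical analysis plan. This does not cure the definition: strata of potential dose count still differ by survival and length of stay, so a trend across them is still not dose-response.

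Finally, a proportion of due doses does not answer a question about cumulative dose: a patient who dies after one dose counts as fully adherent. That stands, and is a cost of the change. It is also true that the analysis is supplementary and exploratory.

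**Conclusion.** The point holds as a fault of definition. The protocol fixes adherence as a raw dose count, that count is truncated by two states of the primary outcome, and the resulting strata do not match the stated rationale. A trend across n can arise with no missed doses and should not be read as dose-response.

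The size is modest. If the eight-dose GM-CSF group were set against all placebo under no effect, the false benefit is about 1.9 points on Table 2 and about 1.6 to 4.5 points with early deaths scaled to 45% mortality and 0 to 6% discharged by day 7. With the threshold in both arms, drift depends on GM-CSF acting mainly early or mainly late, and it can go in either direction. The scaling, discharge range, ICU-exit share, frailty and hazard ratios are assumptions that the protocol does not supply. The primary treatment-policy estimand is unaffected.

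**What to change.** In the Section 9 text on supplementary estimands and in Supplementary Table C:

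- Define adherence as doses received divided by doses due, a dose being due on each of the eight dosing days on which the participant is alive and in hospital. State explicitly that a missed ward dose counts as due.
- Treat death and hospital discharge as separate intercurrent events, not as non-adherence.
- Keep treatment-related stops, such as the white-cell-count stop, as discontinuation. Do not remove those doses from the denominator: GM-CSF can itself cause that stop, and the denominator would then differ by arm.
- Apply the identical rule to placebo doses.
- State that any graph by dose count is descriptive and not evidence of dose-response.

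The cost is wording in the protocol and the analysis plan. It needs dose, discharge and death dates, and no extra patients or visits; no dosing or stopping rule changes. The proportion measures adherence and not cumulative dose, principal-stratum assumptions are still needed, and some link with recovery remains where ward doses are missed after ICU discharge.
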